10.3.1.1 Relevant Subset

The target population is comprised of patients with unilateral upper extremity lymphedema, secondary to breast cancer treatment, who plan to undergo VLNT.

10.3.1.2 Measurement Definition

LymQoL survey is a validated, self-reported outcome questionnaire, developed by experienced healthcare professionals in the lymphedema service in the UK (Keeley, *et al*, 2010). Questions cover four areas: symptoms, body image/appearance, function and mood. Answers are scored 1 to 4 (less severe to severe). LymQoL survey will be used to assess change as a result of intervention. Change = Month 12 aggregate score - baseline aggregate score). Baseline score is defined as the arithmetic average of values obtained at the 2 qualifying screening visits.

10.3.1.3 Measurement Methods

Participants will complete the LymQoL survey at each visit, starting with S1 visit through Month 12. The LymQoL will be completed prior to performance of efficacy assessments (volume measurements, skin caliper measurements, L-Dex BIS).

10.3.1.4 Measurement Time Points

LymQoL surveys will be administered at baseline to Month 12 follow-up visit (Month 3, 6, 9, 12).

10.3.1.5 Response Review

Results will be evaluated by a designated, independent, blinded reviewer.

10.3.2 Change in lymphatic flow function

Change in lymphatic flow function by serial radionuclide lymphoscintigraphy (LSG).

10.3.2.1 Relevant Subset

The target population are participants with unilateral upper extremity lymphedema, secondary to breast cancer treatment, who plan to undergo VLNT.

10.3.2.2. Measurement Definition

For LSG, a significant improvement in the scintigraphic uptake of the transplanted LN (continuous variable); improvement in the uptake of the radionuclide in a defined region-of-interest (ROI) within the proximal LN drainage pathway (axilla); improvement in the reduction of scintigraphic density in a defined ROI for dermal backflow, and improvement in the disappearance rate constant from the injection site.

10.3.2.3 Measurement Methods

LSG: Universal protocol (correct patient, site, procedure) will be adhered to prior to instigation of procedure. After bilateral fingers webs are prepped in a sterile manner, technetium 99m-labeled colloid (radioactive tracer) is injected intradermally around the web spaces of the second and fourth digits (total of 4 point injections). Immediate and delayed (2 hours and 4 hours) static planar images are obtained.

10.3.2.4 Measurement Time Points

LSG will be performed at baseline and 12 months post procedure

10.3.2.5 Response Review

LSG will be evaluated by the co-investigator, [name], MD, Chief of Nuclear Medicine, who will be blinded the subjects' treatment status.

10.3.3 Change in L Dex bioimpedance

Change in L-Dex bioimpedance spectroscopy (L-Dex BIS), from baseline to Month 12, in the intervention group relative to control group.

10.3.3.1 Relevant Subset

The target population are participants with unilateral upper extremity lymphedema, secondary to breast cancer treatment, who plan to undergo VLNT.

10.3.3.2 Measurement Definition

L-Dex BIS value of the affected limb at study end (Month 12) will be compared to pre-intervention value. Baseline value is defined as the arithmetic average of values obtained at the two qualifying screening visits. Mean difference L-Dex BIS values in the intervention group relative to control group at study end (Month 12) following surgical intervention will be evaluated.

10.3.3.3 Measurement Methods

L-Dex BIS utilizes transcutaneous transmission of a very low frequency, subliminal electrical current to determine extracellular fluid volume. It is a form of widely used body composition analysis.

After cleaning the skin (to remove body oils), electrodes are placed on top of the skin of the limb being measured (for arms, at wrist and top of arm). A 4-electrode configuration will be used to non-invasively assess the extracellular and intracellular fluid contents of the limb. The probes are attached to the electrode itself. Measurement setting is selected and the bioimpedance at an extrapolated frequency = 0 (R_0) correlates to the volume of extracellular fluid. The applied current used is 200uA RMS, at a variable frequency of 4 kHz to 1000 kHz.

Participant data will be entered into the device software (encrypted research-dedicated laptop). Data will be analyzed according to Cole theory, using the manufacturer's software (ImpediMed Ltd.), to provide values for a bioimpedance ratio (Ro), the resistance of the extracellular fluid including lymph, R^∞ the resistance of total tissue fluid and R_i , the resistance of the intracellular fluid. For unilateral lymphedema, the ratio of Ro in the affected:unaffected limbs will be analyzed as a measure of the bioimpedance attributable to the extracellular fluid content. Ro level of 1.034 is considered normal; values ≥ 1.034 are considered abnormal. Efficacy profile in lymphedema has been widely documented and this technology is currently utilized for subclinical lymphedema screening of the relevant cancer survivor population in the Stanford Cancer Institute.

10.3.3.4 Measurement Time Points

L-Dex BIS will be performed at screening evaluations to scheduled follow-up visits (Month 3, 6, 9, 12).

10.3.3.5 Response Review

Results will be evaluated by a designated, independent, blinded reviewer.

10.3.4 Change in cutaneous histological architecture

Change in cutaneous histological architecture, from baseline to Month 12, in the intervention group.

10.3.4.1 Relevant Subset

The target population are participants with unilateral upper extremity lymphedema, secondary to breast cancer treatment, who plan to undergo VLNT.

10.3.4.2 Measurement Definition

Quantitative assessment of paired histological specimens of lymphedema skin pre- and post-intervention. The impact of intervention on cutaneous histopathology will be evaluated through the use of an empirically-derived scoring system (comprised of dermal thickness, intercellular mucin content, deep dermal collagen content, and perivascular infiltrate); this quantitative assessment was developed and will be performed by a dermatopathologist. Each characteristic will be weighted equally and each specimen will be assigned a cumulative subscale score of 0 to 5 (normal to severe). The scores were summed for a total score (range: 0 to 20) which is presented here. Higher scores indicate a higher degree of pathology.

A quantitatively higher negative change indicates a more favorable therapeutic response in the histology.

10.3.4.3 Measurement Methods

Standard protocol (correct patient, site, procedure) will be adhered to prior to instigation of surgical procedures. After consent is obtained and completion of time-out, area will be prepped in a sterile manner, area anesthetized, and skin punch biopsies of the affected arm will be performed (optional for control group) by PI. Two 6 mm full-thickness skin punch biopsy specimens will be obtained from the medial aspect of the forearm of affected limb, with an Acu-Punch (Fort Lauderdale, FL) disposable device. Biopsy specimens will be immediately placed in formalin, or an OCT (optimal cutting temperature compound), or frozen for RNA analysis (will not be used for sequencing analysis). Skin punch biopsy will be performed at baseline and at Week 48 visit.

Paraffin-embedded tissue sections will be stained with hematoxylin-eosin (H&E, Richard-Allan Scientific, USA); goat polyclonal anti-LYVE-1 antibody (1:200, Santa Cruz Biotechnology, USA); cutaneous lymphatic microvascular area will be quantitated through immunohistochemical staining of podoplanin with anti-D2-40 antibody (Dako IS072). Tissue

samples will be sliced in 10 μm -thick sections, and evaluated microscopically.

The impact of treatment on cutaneous histopathology will be evaluated through the use of an empirically-derived scoring system (comprised of dermal thickness, intercellular mucin content, deep dermal collagen content, and perivascular infiltrate); this quantitative assessment was developed by a Stanford dermatopathologist published lymphedema studies. The dermatopathologist for this investigation will be blinded to participant treatment status. Each characteristic will be weighted equally and each specimen will be assigned a cumulative subscale score (0 to 5) will be summed for a total score (0 to 20); higher scores indicate a greater degree of pathology. A quantitatively higher negative change will indicate a more favorable histological therapeutic response.

10.3.4.4 Measurement Time Points

Pre- and post-intervention (Month 12) skin punch biopsies, of affected limb will be performed.

10.3.4.5 Response Review

Histology will be assessed by a dermatopathologist blinded to the participant's treatment status.

11. REGULATORY CONSIDERATIONS

11.1 Institutional Review of Protocol

The protocol, the proposed informed consent and all forms of participant information related to the study (eg, advertisements used to recruit participants) will be reviewed and approved by the Stanford IRB and Stanford Cancer Institute Scientific Review Committee (SRC). Any changes made to the protocol will be submitted as a modification and will be approved by the IRB prior to implementation. The Protocol Director will disseminate the protocol amendment information to all participating investigators.

11.2 Data and Safety Monitoring Plan

The Stanford Cancer Institute Data and Safety Monitoring Committee (DSMC) will be the monitoring entity for this study. The DSMC will audit study-related activities to determine whether the study has been conducted in accordance with the protocol, local standard operating procedures, FDA regulations, and Good Clinical Practice (GCP). This may include review of the following types of documents participating in the study: regulatory binders, case report forms, eligibility checklists, and source documents. In addition, the DSMC will regularly review serious adverse events and protocol deviations associated with the research to ensure the protection of human subjects. Results of the DSMC audit will be communicated to the IRB and the appropriate regulatory authorities at the time of continuing review, or in an expedited fashion, as needed.

11.3 Data Management Plan

The Protocol Director and his research team will prepare and maintain adequate and accurate participant case histories with observations and data pertinent to the study. Study specific

Case Report Forms (CRFs) will document treatment outcomes for data analysis. Case report forms will be developed using the Oncore database system and will be maintained by Principal Investigator and his research team. CRFs (paper documents) will be kept in a secure location, not accessible to the public.

12. STATISTICAL CONSIDERATIONS

12.1 Statistical Design

This study is open-label due to visibly apparent differences between the recipients of the surgery.

Primary Endpoint:

The primary outcome is the post-surgical % change in excess limb volume, measured at 12 months, following the surgical procedure.

Secondary Endpoint:

For secondary endpoint, the mean response of the intervention group will be compared to the control group, for change in measurement of dermal thickness, as measured by caliper skin fold thickness, from screening evaluations to Month 12.

12.1.1 Randomization

A blocked randomization design will be used for randomization. Sixty subjects will be randomized in a 4:1 ratio to the intervention arm (VLNT + BioBridge) or control arm (VLNT alone).

12.2 Interim analyses

Not planned.

12.3 Descriptive Statistics and Exploratory Data Analysis

Not planned.

12.4 Primary Analysis

Limb circumference of the affected and unaffected limbs of each participant will be measured for calculation of the volume of the arm through the truncated cone formula.²³ Circumferential measurements of each limb will be obtained with a low stretch gauged tape measure applied at specified intervals of 4 cm (starting from the 3rd metacarpal head) along the axis of the arm, beginning at the wrist. Anatomic landmarks are recorded to facilitate reproducibility between pre- and post-surgical measurements. This method is inexpensive, reproducible, and easily applied. These measurements will be performed at initial evaluation and at each scheduled follow-up visit. The pre-surgical baseline volume for each limb will be defined as the average of the two measurements obtained on study day S1 and study day S2. For quantitative analysis, the excess volume of the limb is defined as the arithmetical difference between the affected

limb (L_{pre}) and the contralateral normal limb (C_{pre}) and the % excess volume at the beginning of the study is defined by:

$$100\% * [(L_{pre} - C_{pre})/C_{pre}].$$

The primary outcome is defined the post-surgical % change in excess limb volume:

$$100 * \{1 - [(L_{post} - C_{post})/(L_{pre} - C_{pre})]\}$$

Analysis Population

Participants are randomized into 1 of 2 arms, the intervention arm (VLNT with BioBridge) or control arm (VLNT-only). The primary analysis will include all participants who have completed all required study visits. However, for participants who do not complete the study, their data will be censored and analyzed with the current population. Treatment summary and adverse event data will also be provided for each treatment category separately.

Efficacy and safety analyses will be performed on all participants who have undergone VLNT (with or without BioBridge). The primary analysis will include all participants who have completed all required study visits and procedures. However participants who do not complete the study will be censored and their data will be analyzed, along with ongoing participants. Data including adverse event data will be captured for each treatment category separately.

Analysis Plan

The final analysis will be undertaken after the final enrolled participant completes all planned study events. At that time, the data will be unblinded and the analyses will be undertaken as described above. There will be multiple analysis populations. The primary analysis will use all subjects enrolled and assigned to treatment, categorized by their planned treatment. A sensitivity analysis will use the set of subjects enrolled and treatment-assigned in the study who completed the study protocol, categorized according to treatment actually received.

Generalized linear mixed effects models are maximum likelihood based methods that are ideal for handling missing outcome data. More specifically, in prospective clinical trials such as the one proposed, a major concern is loss to follow up. The model we have proposed accommodates anticipated loss to follow up and allows us to analyze subjects treated in the study even if they are lost to follow up, ie, if a subject is lost to follow up, the subject is included in the analysis if at least one post-baseline value is recorded prior to loss to follow up). This model relies on a flexible assumption about the missing data, namely that the missing values are missing at random (ie, that missingness is related to observed values only such as baseline volume values and treatment arm). Given the nature of the data generated, we believe this to be a reasonable assumption.

To allow for the possibility that the response variable may not have a linear relationship with the time variable, we will treat time as a categorical variable to allow time to have a non-linear relationship with the response. The categorical time variable can take on values of 3, 6, 9, or

12 months. We will conduct the primary analysis to evaluate whether there is a difference between the treatment and control arms in the volume reduction of the affected limb at 12 months. We will fit the linear mixed effects model below assuming an AR(1) covariance structure. We will evaluate the sensitivity of our assumption about the covariance structure by assuming an unstructured covariance in a sensitivity analysis. Let Y_{ij} represent the reduction in volume of the affected limb for subject i at time j (for $j = 3, 6, 9$, and 12 months), γ_i be the random intercept for subject i , ϵ_{ij} be the error for subject i at time j , trt_i be an indicator for whether subject i is in the BioBridge arm, and $m3_{ij}$; $m6_{ij}$; $m9_{ij}$; $m12_{ij}$ be indicators for whether a measurement on subject i at time j was taken at Month 3; 6; 9; or 12, respectively. To assess whether there is a volume reduction of the affected limb at 12 months, we will test the null hypothesis that $\beta_1 + \beta_7 = 0$ vs the alternative hypothesis of $\beta_1 + \beta_7 \neq 0$.

$$Y_{ij} = \beta_0 + \gamma_i + \beta_1 trt_i + \beta_2 * m6_{ij} + \beta_3 * m9_{ij} + \beta_4 * m12_{ij} + \beta_5 * m6_{ij} * trt_i + \beta_6 * m9_{ij} * trt_i + \beta_7 * m12_{ij} * trt_i + \epsilon_{ij}$$

We will also perform a sensitivity analysis where we only include subjects with complete data who can provide quantitative changes. Such an analysis relies on an assumption that the data are missing completely at random, an assumption that we do not feel is practical in most clinical trial settings and certainly not here. The motivation for performing this analysis; however, allows us to assess how robust our findings are to deviations in our assumptions of missingness. A final sensitivity analysis will be performed where we impute data using multiple imputation techniques that rely on an assumption that the data are NOT missing at random. More specifically, our imputation model will assume those with missing values in the treatment arm are less likely to have a salutary treatment effect. Such sensitivity analyses will provide a context in which we can appropriately interpret the primary findings. In this sensitivity analysis, we will assume a range of volume reductions in the treatment arm (eg, 90%; 75%; 50% of the reduction observed in the control arm). If we find a statistically significant reduction in the treatment arm as compared to the control arm, the range of reductions will be chosen such that the range covers the “tipping point” where the difference in the two arms is no longer statistically significant. This “tipping point” analysis is in place of a worst-case sensitivity analysis because there is not a clearly defined “worst-case” in a non-binary outcome. Our sensitivity analysis will follow the advice given in “Strategy for intention to treat analysis in randomized trials with missing outcome data.”²⁵

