4. TREATMENT PLAN

Pre-op procedure:

- LSG baseline (it may be the same as one performed for research purposes)
- Venous duplex to evaluate the superficial and deep venous systems for clots and valvular insufficiency
- ICG fluorescence lymphatic mapping to assess the superficial lymphatic system
- Labs: CBC, CMP, PT/PTT, EKG, CXR
- Research samples: blood and skin samples; optional for control group
- Baseline photograph of limbs

Post-op:

- LSG at 12 months (it may be the same as one performed for research purposes)
- ICG fluorescence lymphatic mapping at 12 months

- Research samples: blood and skin samples; skin biopsies are optional for control group
- Photograph at 12 months

Time of procedure:

Operating time ~6 hours, additional 45 min for BioBridge placement; anesthesia ~10 to 12 hours, positioning, IV and arterial line placement, OR, etc (time is variable).

Description of procedure:

On the day of surgery, the patient will be sent to radiology for injection of Technecium-99 in the second web space of bilateral feet or contralateral arm in preparation for intraoperative lymph node transfer. Patient will be marked in the preoperative area. Patient will then be taken to the operating room, placed on the operating room table in the supine position with both arms abducted. Perioperative antibiotic will be given on-call to the OR. After general endotracheal anesthesia is established, the entire anterior chest, abdomen, proximal thighs and arm(s) will be prepped and draped in the usual sterile fashion. A surgical pause is taken to identify the patient and the procedure(s) to be performed.

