Attention will be turned to the left or right groin lymph node region or right or left neck for supraclavicular lymph node region. A Doppler is used to confirm the location of the lymph node pedicles. Next, reverse lymphatic mapping is used as an additional method to confirm the location of the lymph nodes. Technecium-99 will be injected preoperatively into the foot or hand (depending on donor site). A gamma probe is used to localize the sentinel lymph node draining the extremity, which will be avoided during flap harvest. The highest gamma probe count is noted and the donor site is deemed suitable only if the gamma probe count for the planned lymph node donor site is <10% of the previously noted maximum. Indocyanine green (ICG) 0.2 mL is injected intraoperatively into several sites along the periphery of the donor flap (lower abdomen or supraclavicular) for lymphatic mapping. Fluorescence angiography is used to visualize the lymph nodes draining the lower abdominal wall or supraclavicular region.

Groin donor flap:

The lymph nodes draining the lower abdomen are visualized and correlated with the SCIA-based lymph nodes. An incision is made into the lower (left or right) abdomen and the skin flaps are elevated just above the Scarpa fascia. At the superior edge of the flap, the SCIV and SIEV are both identified and divided, with the knowledge that most of the target lymph nodes will lay between these vessels. The flap will be elevated lateral to medial just above the sartorius fascia. The SCIA branch to the Sartorius muscle is divided, and the SCIA and branches of the SCIV are mobilized to their origin and are harvested for transfer.

The groin wound is irrigated with an antibiotic solution and hemostasis is achieved. The inguinal fascia, if needed, may be reinforced with an onlay polypropylene mesh, secured with interrupted and running 2-0 Prolene sutures. A Blake drain will be placed to drain the groin

wound. The wound is closed with interrupted 2-0 Vicryl sutures for the Scarpa, interrupted 3-0 Vicryl sutures for the dermis and 4-0 Monocryl running subcuticular stitch.

Supraclavicular donor flap:

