4.1 General Concomitant Medication and Supportive Care Guidelines

For VLNT, the following is routinely used pre-operatively (standard of care, SOC):

Chlorhexidine gluconate scrub.

Anesthesia risks (anesthesia and intubation) (SOC for VLNT placement; research for BioBridge placement):

Intubation injury; aspiration; anesthesia awareness; difficulty breathing after surgery; malignant hyperthermia; reaction to anesthesia drugs; nausea; vomiting; dry mouth; sore throat; shivering; sleepiness; confusion; hoarseness.

For VLNT, the following medications are routinely used intra-operatively (SOC for VLNT placement; research for BioBridge placement):

Midazolam; fentanyl; lidocaine; propofol; rocuronium; dexamethasone; ketamine; hydromorphone; acetaminophen; ondansetron; antibiotic (usually cephalexin unless allergic); scopolamine; magnesium; IV fluids (saline, lactated ringers).

Arterial line risks (SOC): Bleeding; hematoma; thrombosis; infection.

Rare risks: permanent arterial occlusion; pseudoaneurysm, sepsis.

Surgical risks (SOC for VLNT placement; research for BioBridge placement):

Bleeding; deep vein thrombosis (DVT); delayed healing; death; infection; injury during surgery; medical complications (pneumonia; MI; CVA; itching; scarring; numbness; neurovascular injury; tingling around surgical site(s); pain; persistent edema; seroma; flaps loss; donor site lymphedema; bruising; and need for reoperation.

For VLNT, the following medications are routinely used post-operatively (SOC):

Oxycodone; aspirin; ondansetron; Bacitracin zinc ointment; Lovenox; hydromorphone; heparin infusion

Lymphoscintigraphy (SOC for VLNT placement; research for BioBridge placement):

LSG will be performed for both research purposes and standard of care (1-2 scans pre-surgery and 1 to 2 scans 12 months post-surgery).

Lymphoscintigraphy requires four injections of 250uCi Sulfur Colloid, is performed at baseline and 12 months after surgery, and involves exposure to radiation. The LSG for research are not necessary for medical care. The additional amount of radiation exposure is about 7 mSv, which is approximately equal to 14% of the limit that radiation workers (for example, a hospital X-ray

technician) are allowed to receive in 1 year. This amount of radiation involves minimal risk and is necessary to obtain the research information desired.

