10.1.3 Measurement Methods

Limb volume quantification, of affected and non-affected limbs, will be performed using circumferential measurements of the limb, at 4 cm intervals beginning at the wrist. The limb volume will be determined using a truncated cone formula{volume = $\pi h(R^2 + Rr + r^2)/3$, let h be the height, R the radius of the lower base, and r the radius of the upper]. Limb circumference, for calculation of limb volumes, will be serially measured at screening evaluations and in follow-up to study end (Month 12). For quantitative analysis, the volume of the ipsilateral arm will be expressed as a percentage of the unaffected arm volume and of the pre-treatment volume of the ipsilateral arm.

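### Under the section 12.4 formula, swelling of the contralateral arm after a neck-node harvest on that side would count as improvement, and no planned comparison would flag it

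*Combined protocol and SAP*

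**What the plan says.** The surgical risks in section 4.1 include "donor site lymphedema; bruising; and need for reoperation". Section 4 (Description of procedure) lets the nodes come from the "left or right groin lymph node region or right or left neck for supraclavicular lymph node region". Preparation includes "injection of Technecium-99 in the second web space of bilateral feet or contralateral arm", so that the node draining the donor extremity can be located and spared. The plan therefore treats the legs as the limbs at risk for a groin harvest, and the contralateral arm as the limb at risk for a neck harvest on that side.

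Scheduled measurement is confined to the arms. Section 10.1.3 says: "Limb volume quantification, of affected and non-affected limbs, will be performed using circumferential measurements of the limb, at 4 cm intervals beginning at the wrist". Caliper sites are on the hand, forearm and upper arm (10.2.3), bioimpedance compares the two arms (10.3.3.3), and the Study Calendar (section 9) lists no leg measurement.

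Section 12.4 says: "The primary outcome is defined the post-surgical % change in excess limb volume". The formula is `100 × {1 − [(L_post − C_post)/(L_pre − C_pre)]}`, where L is the affected arm, C is the contralateral arm, and each baseline is the mean of S1 and S2.

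Two other places use a different outcome. Section 10.1.2 compares the affected limb with its own baseline. The mixed model in the Analysis Plan of 12.4 takes Y as the reduction in affected-limb volume. Neither has a contralateral term.

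**The concern.** The formula relies on the contralateral arm as a stable reference that corrects for general change such as weight. A neck harvest on that side can make the reference arm itself the injured limb. If it swells, the difference L_post − C_post shrinks and the patient scores as improved, so harm to a healthy limb would be entered as efficacy.

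No section compares C_post with C_pre, and section 12.3 plans no descriptive statistics in which such a change would show. The bioimpedance ratio in 10.3.3.3 would not expose it either, because fluid in the unaffected arm also moves that ratio toward parity. After a groin harvest the harm does not enter the formula, but it is not objectively measured.

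The stake is mainly safety reporting: the trial could conclude that donor-site lymphedema did not occur without having looked for it in the measurements. The second stake is the meaning of an individual score.

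**Working it through.** **1. The plan's own figure.** Inputs from 12.6.2: SD 19 points, 48 versus 12 patients, alpha 0.05 (two-sided, as in the 12.4 hypothesis), power 0.9.
- Standard error of the difference = 19 × √(1/12 + 1/48) = 6.1 points.
- Detectable difference = (1.960 + 1.282) × 6.13 = 19.9 points. Power for 20 points is 0.903 by the normal approximation. The stated 20% is reproduced.

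**2. Effect of contralateral growth on one score.** Let e = (L_pre − C_pre)/C_pre and C_post = C_pre × (1 + g). Compared with an unchanged reference arm, the numerator L_post − C_post falls by g × C_pre, so the score rises by

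`100 × g × C_pre/(L_pre − C_pre) = 100 × g/e` points,

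whatever the affected arm does. Section 3.1.12 sets the minimum e at 20%. All values of g, and of e above 20%, are assumptions.

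| Growth g | e = 20% | e = 40% | e = 50% |
|---|---|---|---|
| 2% | 10 | 5 | 4 |
| 4% | 20 | 10 | 8 |
| 5% | 25 | 12.5 | 10 |
| 10% | 50 | 25 | 20 |

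Example: C = 2000 mL and L = 2400 mL, so the excess is 400 mL. If L stays the same and C rises to 2080 mL, the excess is 320 mL and the score is 100 × (1 − 320/400) = 20, although the affected arm has not changed.

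**3. Effect on the arm means.** One patient with 4% growth at e = 20% moves the control mean by 20/12 = 1.7 points, or 0.27 of the standard error in step 1. The same patient in the BioBridge arm moves that mean by 20/48 = 0.4 points.

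**4. How many cases to expect.** Section 4.1 (Stanford Experience) reports none in more than 100 procedures. Read as 0 of 100, the 95% upper limit is 1 − 0.05^(1/100) = 3.0% one-sided, or 1 − 0.025^(1/100) = 3.6% two-sided. At 3.6% the expected count is 60 × 0.036 = 2.2 patients overall and 12 × 0.036 = 0.4 controls, for all donor sites together. The documents give neither the share of neck donors nor how donor limbs were assessed in that series.

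**5. What the sensitivity version does.** With C_pre in place of C_post the score becomes `100 × (L_pre − L_post)/(L_pre − C_pre)`. Contralateral growth drops out, and the 20 points in the example return to 0.

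**The case against.** Several counter-arguments have force.

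- **The harm is not invisible.** Physical examination is listed at T1–T4 for everyone and at T6–T7 for BioBridge recipients, with symptom and adverse-event review at T1–T7 (section 4, Study Visits). Patients have round-the-clock contact (7.1), and events are CTCAE-graded (7.2). The contralateral arm is also taped at each visit through T5, and section 12.5.2 generates an L-Dex score for each limb. This stands: data on that arm will exist. What is missing is a pre-specified comparison that uses them.
- **Harvest is designed to avoid it.** The donor extremity's sentinel node is spared, and a site is used only if its gamma count is low enough (section 4). This stands, and it fits the low expected count.
- **The score inflation depends on which definition governs.** Under 10.1.2 and the model's Y there is no C_post and no inflation. This stands too. But the synopsis and sections 1.1, 12.1 and 12.4 name excess volume, and 12.4 gives the only formula for change in excess volume, so the conflict has to be resolved rather than used as a defence.
- **The neck side is not fixed.** The donor text allows either side. The contralateral case is inferred from the tracer site, and an ipsilateral harvest would leave the reference arm out of it.

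A reader might also infer that the trial is biased in favour of BioBridge. The documents do not support this. Both arms undergo VLNT, and a swollen reference arm in a control would raise the control mean and work against the device. Donor site is not a stratification factor (3.4), but randomisation still balances it in expectation. Nor should one patient's 20 points be equated with the 20-point design difference, which is a difference between group means.

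**Conclusion.** The point holds in limited form. The direction is certain from the 12.4 formula: growth of the contralateral arm adds 100 × g/e points, for example 20 points at g = 4% and e = 20%, or 10 points at e = 40%. The growth figure is assumed.

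The inflation applies only to neck harvests on the contralateral side, and only if the 12.4 formula governs. For groin donors the harm is unmeasured, not scored as benefit. With few cases expected and 1.7 points per affected control against a standard error of 6.1, it is unlikely to drive the primary result. It is a gap in objective safety detection and a weakness of the endpoint formula, worth closing because the arm data are already collected.

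**What to change.** 1. **Reconcile the outcome definition.** State whether the primary outcome is change in excess volume (the 12.4 formula) or reduction in affected-limb volume (10.1.2 and the model's Y), and use one definition throughout.
2. **Use the contralateral-arm data for safety.** Record donor site and side. At T1–T5, tabulate each patient's contralateral-arm change from the S1/S2 baseline by study arm. Refer growth beyond measurement repeatability to adverse-event review as possible donor-site lymphedema. Repeatability could be estimated from the paired S1 and S2 contralateral volumes. Borrowing the 10% screening tolerance of 3.1.12, which was set for the affected limb, would miss the 4% case above.
3. **Add a sensitivity analysis** of the primary endpoint with C_pre in place of C_post.

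The cost is SAP and CRF wording; no visit or procedure is added. The downside of item 3 is that it loses the correction for whole-body change. If both arms grow by an assumed 2% at e = 20%, the 12.4 formula moves by −2 points, but the C_pre version moves by −100 × 0.02 × 1.2/0.2 = −12 points. It should stay a sensitivity analysis, read beside the weights already recorded.

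Two further steps are not recommended here. Taping the legs is an added procedure, and because donor-site suitability is confirmed only at surgery, a baseline might be needed in every patient. Splitting efficacy by donor site would divide 12 controls into groups too small to interpret.
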